#### Primary Hypothesis (Specific aim 1, Hypothesis 1b)

A test of the primary null hypothesis, that PAP intervention does not increase mean PASAT score against the 1-sided alternative hypothesis that PAP intervention increases mean PASAT, will be based on a general linear model (GLM). PASAT score is modeled as a function of PAP intervention, using an indicator variable with 1 indicating PAP and 0 the sham treatment. A 1 degree of freedom test based on an F statistic will be used to test for a positive coefficient for the PAP indicator. This modeling approach provides a unified framework that accommodates covariates including use of sedating medications, years of education, level of injury, duration of injury, pain severity, presence of anxiety or depression, compliance with PAP, and recruitment center, each of which may reasonably be anticipated to influence PASAT score. We plan to include these covariates in our primary hypothesis test, which will be carried out at  $\alpha = 0.05$ . If the null hypothesis of no effect is rejected, computation of 95% confidence limits on the estimate of treatment difference in PASAT score mean will be carried out.

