### Objectives/Specific Aims/Hypotheses

The proposal describes a multi-center double blinded, placebo controlled randomized trial (RCT) designed to examine the impact of SDB treatment in persons with chronic SCI. The **central hypothesis** is that the treatment of SDB with PAP will improve cognition, sleep quality, HRQOL, and CVD surrogate measures in persons with chronic SCI. The specific aims and hypotheses of the proposed research are:

Specific Aim 1	
Determine the associations between sleep disordered breathing (SDB) and cognitive impairments in chronic SCI and the impact of PAP therapy on cognitive measures in a cohort with chronic SCI and SDB.
 
Hypothesis 1a: Compared with patients without SDB, patients with SDB will exhibit more severe and widespread cognitive impairments (in memory, attention, and executive function), while controlling for depression, pain severity, duration of injury, level of injury, sedative use, and pre-morbid intelligence
 
Hypothesis 1b: SCI participants who are randomized to four months of therapeutic PAP will show improvement in cognitive measures (memory, attention, and executive function) compared with those receiving sham PAP.

Specific Aim 2	
Determine the impact of PAP therapy on surrogate CV biomarkers, sleep quality, quality of life, mood, and pain in a cohort with chronic SCI and SDB.
 
Hypothesis 2a: SCI participants randomized to four months of PAP will show an improvement in CV biomarkers (hs-CRP, TNF-a, VCAM-1, adiponectin, and 8-isoprostanate) compared with sham PAP.
 
Hypothesis 2b: Sleep quality, quality of life, mood, and pain will improve in SCI participants receiving PAP and stay the same or worsen in those randomized to sham PAP.

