## Research Strategy and Study Design

### Study Overview:

During the 4-year study period we will screen 200 SCI participants who meet eligibility criteria and consent to participate with portable level II polysomnography (PSG) and randomize 100 subjects who have SDB to auto-PAP or sham PAP. Participants will be recruited from the University of Miami (Miami Project to Cure Paralysis), the Miami VA, Wayne State University (Michigan Rehabilitation Institute), and affiliated Detroit VA through their outpatient SCI clinics and/or inpatient rehabilitation units. Participants will be asked to complete questionnaires measuring sleep quality (SQ), SDB risk, insomnia severity, daytime sleepiness, pain severity, mood, and HRQOL. They will undergo an overnight, at home (or if hospitalized, in the hospital room) portable unattended PSG performed at their normal sleep time. Subjects with an apnea-hypopnea index (AHI)  $\geq 10$  events/hr will be randomized to receive 4 months of auto-PAP therapy or PAP set at a fixed pressure of 3 cmH20 (sham PAP).

We will perform neuro-psychological evaluations prior to randomization on all participants who complete a portable PSG to evaluate general and pre-morbid function, immediate verbal memory, simple and sustained attention, processing speed, and executive function. Selection of these particular cognitive measures reflects impairments in these domains observed in patients with SDB within the general population. These domains are also impaired in patients with acute and chronic SCI. **Importantly, none of the cited SCI studies have examined the potential role of SDB in cognitive impairment in SCI participants.**

One cognitive measure (PASAT) and 3 sleep questionnaires (PSQI, FOSQ and ESS) will be repeated at 1 month follow-up in those randomized to therapy or placebo. Complete neuro-psychological evaluations will be repeated at the 4 month follow-up time point in those with SDB who were randomized to PAP or sham PAP (primary outcomes). All measures obtained from these repeated assessments will be subject to a Reliable Change Index analysis to control for potential practice effects. We will obtain blood and urine samples for measurement of CV biomarkers at time of randomization and the four month follow-up. Additionally, sleep and quality of life questionnaires will be repeated at four month follow-up (secondary outcomes).

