**Baseline Measurements All Subjects:** At the Miami and Detroit sites the study RA will approach SCI individuals identified by the study PI and Co-investigators to determine eligibility for participation in the study. Upon consent, we will ask participants to complete several questionnaires detailed below. We will schedule participants for a single night unattended portable home PSG within one week of enrollment to evaluate sleep architecture and diagnose SDB. The RA at each site will review medical records to document medical and psychological co-morbidities, medication use, laboratory data, spinal cord injury level, ASIA classification, and duration of injury. We will interview participants during their enrollment visit to obtain a medical/sleep history, and anthropometric measures (height, weight, neck circumference, and abdominal girth at end expiration). Whenever possible the RA or PI/site PI will complete the international SCI core dataset for each participant. Additionally, we will use the international SCI CV function basic data set to obtain information about CV co-morbidity. Cognitive testing will be completed at baseline on all subjects who complete portable PSG. **Figure 2 outlines study flow and measurements.**

We will obtain the following respiratory measures during PSG: a) AHI: defined as the number of apneas and hypopneas per hour of sleep, b) arousal index (AI): the number of arousals per hour of sleep, c) percentage of total sleep time (TST) spent with arterial oxygen saturation (Sa-O2) < 90%, d) mean minimum Sa-O2, and e) oxygen desaturation index 4% (ODI4), defined as the number of four percent desaturation events per hour of study time. Respiratory and sleep architecture definitions will be scored according to accepted criteria put forth by the American Academy of Sleep Medicine (AASM). We will define SDB as an AHI  $\geq 10$ . We will score hypopneas initially using alternative rules (>50% reduction in airflow with 3% desaturation or arousal). We will rescore using recommended rules (>30% reduction in airflow with 4% desaturation). In the sleep research community, there is currently no clear consensus on which scoring method is preferred. SDB prevalence rates reported in the literature differ depending on the definition used. Consequently, we will perform all analyses with both definitions in mind and report any differences in observed associations.

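### The primary PASAT model, and the between-arm secondary models that reuse it, leave out the baseline value of the outcome although it is collected

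*Combined protocol and SAP*

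**What the plan says.** The primary test is set out under Primary Hypothesis (Specific aim 1, Hypothesis 1b): "PASAT score is modeled as a function of PAP intervention, using an indicator variable with 1 indicating PAP and 0 the sham treatment". The model "accommodates covariates including use of sedating medications, years of education, level of injury, duration of injury, pain severity", and the list continues to its end with "pain severity, presence of anxiety or depression, compliance with PAP, and recruitment center". That makes eight items. The plan then commits to them: "We plan to include these covariates in our primary hypothesis test". Baseline PASAT does not appear.

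The baseline score exists for everyone randomized. The paragraph Baseline Measurements All Subjects says "Cognitive testing will be completed at baseline on all subjects who complete portable PSG", the Study Overview places this testing before randomization, and the description of the cognitive battery repeats that every test is given at baseline and at four months. For those randomized, the Study Overview adds: "Complete neuro-psychological evaluations will be repeated at the 4 month follow-up time point", and labels these the primary outcomes.

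Secondary Hypotheses bases the comparison of arms at 4 months on the same linear model. Baseline values are used there only for paired tests within each arm. The Biomarkers section and the section Sleep, Quality of Life, and Mood show that baseline values of these outcomes are collected too.

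**The concern.** The plan picks its covariates as factors that can be expected to influence PASAT. A participant's own earlier PASAT score meets that criterion directly, costs nothing to obtain and cannot be affected by treatment. Without it, variation between participants that was already visible at baseline stays in the residual, and the interval for the treatment difference is wider than it needs to be. In addition, any chance difference between arms in baseline PASAT that the listed covariates do not capture carries over into the estimated effect.

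The same loss applies to the secondary outcomes. The within-group paired tests do use baseline, but they do not compare PAP with sham. Pain and mood may be partly covered, because pain severity and presence of anxiety or depression are on the covariate list, but the list gives no time point for them. For biomarkers, sleep and quality of life nothing comparable is listed.

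**Working it through.** **Inputs from the documents** (sample size paragraph under Data Analysis): difference 7 points, SD 9, alpha 0.05, 40 per arm, stated power 0.93, 100 randomized, 40% non-adherence and/or loss to follow-up.

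**The plan's own figure.** A two-sample noncentral t calculation with 40 per arm, difference 7 and SD 9 gives two-sided power of 0.930, which reproduces 0.93. (One-sided, it gives 0.964.) The calculation uses the raw SD of 9, so it takes no credit for any covariate.

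**Assumptions, because the documents do not give them.**
- r, the baseline to 4-month correlation of PASAT: 0.3 / 0.5 / 0.7 / 0.8.
- R², the share of PASAT variance explained by the listed covariates: 0.20, then 0.40.
- The covariates explain the same R² at both visits through the same linear index, and are unrelated to arm.
- The eight items take 8 degrees of freedom.

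**Formulas**, with n per arm:
- Planned model: residual SD = 9 × √(1 − R²), df = 2n − 10.
- With baseline: partial correlation p = (r − R²)/(1 − R²), residual SD = 9 × √((1 − R²)(1 − p²)), df = 2n − 11.
- 95% half-width = t(0.975, df) × residual SD × √(2/n).

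**Worked example**, R² = 0.20, r = 0.7, n = 30. Planned: 9 × √0.80 = 8.05, then 2.009 × 8.05 × √(2/30) = 4.17. With baseline: p = 0.50/0.80 = 0.625, SD = 8.05 × √(1 − 0.391) = 6.28, then 2.010 × 6.28 × √(2/30) = 3.26.

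| R² | n per arm | planned half-width | r = 0.3 | r = 0.5 | r = 0.7 | r = 0.8 |
|---|---|---|---|---|---|---|
| 0.20 | 30 | 4.17 | 4.14 | 3.87 | 3.26 | 2.76 |
| 0.20 | 50 | 3.20 | 3.17 | 2.97 | 2.50 | 2.12 |
| 0.40 | 30 | 3.62 | – | 3.57 | 3.13 | 2.70 |
| 0.40 | 50 | 2.77 | – | 2.73 | 2.40 | 2.06 |

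(At R² = 0.40 and r = 0.3, p would be negative, so no figure is shown.) Thirty per arm treats the whole 40% as lost; 50 per arm keeps everyone randomized.

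**Chance imbalance.** At R² = 0.20, one standard error of the baseline gap left after the listed covariates is 8.05 × √(2/30) = 2.08 points at 30 per arm. Such a gap shifts the 4-month estimate by p × 2.08 = 0.3 / 0.8 / 1.3 / 1.6 points. At 50 per arm the standard error is 1.61 and the shift 0.2 / 0.6 / 1.0 / 1.2.

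**Power.** At R² = 0.20 the planned model has one-sided power for 7 points of 0.95 at 30 per arm and above 0.99 at 50, before baseline is added. If the effect were diluted to 7 × 0.6 = 4.2 points with 50 per arm (a further assumption), power would go from 0.83 to 0.83 / 0.87 / 0.95 / 0.99.

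No figure is given for the secondary outcomes, because the documents state no SDs for them.

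**The case against.** The covariate list is introduced as open-ended, so baseline PASAT is not excluded. That is true, but the commitment covers the named items, and a covariate added later would not be pre-specified. The plan also says "All measures obtained from these repeated assessments will be subject to a Reliable Change Index analysis to control for potential practice effects". This serves another purpose, and nothing ties it to the primary model.

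The benefit could be small. That stands. It ranges from nil to moderate, depending on r and R². The figures are also idealised. They treat every covariate as unrelated to arm, which may not hold for PAP compliance: at an assumed correlation of 0.5 with arm, the planned half-width at 30 per arm would be 4.17/√(1 − 0.25) = 4.8. And since the primary analysis is by intention to treat, non-adherent participants stay in, so 30 per arm is the pessimistic end.

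A reader might infer from Hypothesis 1b, where participants "will show improvement in cognitive measures", that the dependent variable is left undefined between the 4-month score and the change from baseline. The documents do not support that strongly. The Study Overview puts the primary outcomes at 4 months, the sample size is based on a difference in mean scores, the primary test concerns mean PASAT, and Secondary Hypotheses keeps differences from baseline for the within-group tests. Together these favour the 4-month score; what is missing is one line of confirmation.

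**Conclusion.** The point holds as a matter of efficiency and clarity. The primary model omits a baseline covariate that is already collected, and the between-arm secondary models inherit the omission. At R² of 0.20, the half-width shrinks by 0.03 to 1.4 points at 30 per arm (4.17 to between 4.14 and 2.76) and by 0.02 to 1.1 points at 50 per arm (3.20 to between 3.17 and 2.12). At R² of 0.40 the gain is negligible for r up to 0.5. These sizes rest on the assumed r and R² and on covariates unrelated to arm.

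A reader might go further and conclude that the estimate is biased, that type I error is inflated or that the trial is underpowered. The documents do not support this: under randomization, omitting baseline does none of the first two, and power for 7 points is already high under the same assumptions. This reassurance covers only the omission of baseline. It says nothing about the effect of including PAP compliance, which is measured after randomization, in the same model; that is a separate question.

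**What to change.** In a dated amendment made before unblinding:

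- Under Primary Hypothesis, add baseline PASAT as a covariate and confirm in one line that the dependent variable is the 4-month PASAT score. With baseline in the model, the treatment coefficient is the same whether the 4-month score or the change is analysed.
- Under Secondary Hypotheses, add the baseline value of each outcome to its between-arm model.
- State that the pain and mood covariates are the baseline values.

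The cost is wording and one degree of freedom per model. No new data are needed.

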	
function. These deficits are important for day to day activities.
 
SCI participants with SDB may indeed demonstrate worse cognitive impairment in these domains.
 
More study is needed to determine the full extent of the interaction between SDB and SCI and their combined impact on cognitive function.
	
results between those with and without SDB.
 
b) Additionally, other factors that may impact cognitive performance including pain severity, mood, pre-morbid intelligence, duration of injury, presence of insomnia, and use of sedating medications will be measured and included in a multivariable regression model to better delineate the impact of each of these factors and SDB on cognitive impairment.

1 and 2	
Although there is now some data that demonstrate increased prevalence of poor sleep quality and SDB in SCI subjects, there is no clear evidence that treating these conditions will lead to short and long term benefits.
 
PAP is a medically-justified intervention in persons with SDB, but has seen limited use in persons with SCI. Strength of evidence does not currently support screening for SDB and intervention with PAP in persons with SCI.
 
Persons who are prescribed PAP are not always compliant with its use. Compliance in this population has seen limited study.
 
The impact of PAP on cognitive outcomes in chronic SCI is unknown
 
The impact of PAP on surrogate CV biomarkers, mood, and quality of life in this population is unknown.
	
a) The research will determine the effectiveness of PAP in treating SDB in chronic SCI using gold standard research methodology (RCT).
 
b) The research will provide the empirical support necessary to justify treatment of SDB in persons with SCI.
 
c) The research will examine population-specific compliance levels in PAP use, and identify whether compliance influences health-related outcomes.
 
d) Our clinical trial will identify the impact of PAP therapy on cognitive measures, mood, quality of life, and surrogate CV endpoints. All these measures are relevant to the emotional and physical well-being of participants with chronic SCI and will likely have a practical impact on day to day living in this population.

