**Intervention**

All randomized subjects will be fitted with a nasal or full-face mask and head gear. PAP will be delivered by an auto-titrating device (Resmed S9-Autoset, San Diego USA). These devices automatically set the level of delivered pressure to ensure upper airway patency, to treat detected apneas and hypopneas, thereby eliminating the need for a pressure titration sleep study to be performed in the sleep laboratory. Auto-PAP has been successfully used in several patient populations and may improve compliance with PAP. Participants who are randomized to the placebo arm will receive an auto-PAP device that is set to a fixed low pressure of 3 cmH2O without an ability to titrate according to detected respiratory events. The pressure is too low to eliminate respiratory events and serves as sham or sub-therapeutic PAP (placebo PAP). Additionally, six extra

4 mm holes will be cut in the rubber collar of the connecting tubing at the mask end. These extra blow-off holes, together with the standard hole in the PAP mask, allow more air to escape and keep the nasal pressure low while ensuring no CO2 re-inhalation. This method has been successfully and safely used as a placebo in previous RCTs in participants with SDB.

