The auto-PAP machines will record the number and type of respiratory events detected, the pressure delivered in response to these events and the amount of time that the machine was on and delivering pressure to a patient. All subjects will be instructed to use the device nightly during sleep, for the ensuing four months. Objective compliance checks will be conducted at 1 week, 1 month, and study completion, by having the subject present the PAP "Smartcard" for download and interpretation. To increase patient compliance and decrease variance in outcomes introduced from differing degrees of exposure to the intervention, we will employ standardized procedures for management of PAP currently employed at University of Miami PAP clinic. These include instructing subjects on machine and mask use and regular phone follow-up for troubleshooting as necessary. The study PI will review compliance downloads and instruct the Research Associates (RA) to contact participants if compliance is low or machine reported air leakage from mask is too high. This is will be done for both arms of the study. The RA will not be aware of the details of the compliance report or machine pressure delivered to maintain blinding. Daily compliance will be reported as the total number of hours of PAP use per 24 hour period. Patients who use PAP > 4 hours/night for more than 50% of the nights at 4 month follow-up will be classified as PAP compliant.

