#### Secondary Hypotheses

A second phase of analysis will focus on CV biomarkers and measures of sleep quality, quality of life, mood and pain. These analyses are considered exploratory in nature and hence will benefit from comparisons within as well as between groups.

For within group contrasts, initial observations serve as baseline for assessing the effect of treatment at 4 months. As in a classical paired design, inference focuses on the difference between baseline and 4 month observations. Hence, individuals serve as their own control for an effect of intervention. The null hypothesis that the baseline does not differ from the 4 month measurement is tested using statistical methods for a paired design. For normally distributed measurements, a paired t test will be used. For variables that depart from normality and cannot be transformed to approximate normality, a Wilcoxon signed rank test will be used.

Comparisons between PAP and sham treatment groups at 4 months will be made based on the linear model described above for the primary endpoint. In contrast to PASAT, however, tests for treatment group differences of CV biomarkers and measures of sleep quality, HRQOL, mood and pain will be 2-sided. Because the number of secondary hypotheses to be tested is potentially large, these tests will be considered exploratory in nature. Accordingly, control of the false positive inference rate for these tests will be carried out at the group level, as described below, rather than for the entire set of secondary analyses. Similar approach will be taken for the analyses of select measures at the one month time-point.

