#### Control of False Positive Rate of Inference

The inference of primary interest in this study is the effect of treatment on PASAT score. Because the test for intervention on PASAT is considered pre-planned, it will be carried out at  $\alpha$ -level 0.05. Similarly, tests for effects on groups of CV biomarkers, sleep, mood and quality-of-life measurements

are considered pre-planned in the sense that measurements in each group will be subjected to statistical testing regardless of test outcome for PASAT. Accordingly, tests for multiple measurements taken in each category of biomarkers will be carried out at  $\alpha$ -levels below 0.05. This approach recognizes that multiple testing is involved within each biomarker category and adjusts the significance level for individual tests downward to control the false positive inference rate at the category level. We will apply a False Discovery Rate (FDR) criterion of 5% separately for each category, thereby acknowledging the substantial overall number of tests per category but preserving power to detect true effects for each type of biomarker.

Primary analyses will be conducted in accordance with the intention-to-treat principle. We will also repeat analyses using a per protocol viewpoint. We will use statistical software, SPSS for Windows version 19 for all analyses.

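### The primary PASAT test adjusts for PAP compliance, which is measured only after randomisation, so it does not in general test the effect of assignment to PAP

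*Combined protocol and SAP*

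**What the plan says.** The section Primary Hypothesis (Specific aim 1, Hypothesis 1b) models PASAT as a function of a PAP indicator and tests, one-sided, for a positive coefficient. Its covariate list includes "presence of anxiety or depression, compliance with PAP, and recruitment center, each of which may reasonably be anticipated to influence PASAT score". The list is not optional: "We plan to include these covariates in our primary hypothesis test, which will be carried out at" the 0.05 level.

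The section Intervention shows when compliance becomes known: "Objective compliance checks will be conducted at 1 week, 1 month, and study completion". The yes/no class comes at the end: "Patients who use PAP > 4 hours/night for more than 50% of the nights at 4 month follow-up will be classified as PAP compliant". The plan does not say whether hours of use or this class enters the model.

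Under Secondary Hypotheses, "Comparisons between PAP and sham treatment groups at 4 months will be made based on the linear model described above for the primary endpoint", and a similar approach is announced for the one-month measures. Under Control of False Positive Rate of Inference, "Primary analyses will be conducted in accordance with the intention-to-treat principle", with a separate per-protocol repeat.

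**The concern.** Intention-to-treat asks what being assigned to PAP rather than sham does to PASAT. Every available measure of compliance follows assignment and may be changed by it. If it is, compliance lies between treatment and outcome, and holding it fixed changes the question. Two separate things can follow.

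- **Lost effect.** If use differs between arms and PAP works through use, part of a true benefit is credited to the compliance term. This happens even when nothing else links use to PASAT.
- **Wrong error rate.** If use differs between arms and also shares a cause with PASAT that the other covariates miss, comparing patients at equal compliance compares unlike patients. The one-sided type I error then departs from 5%, in a direction that depends on which arm uses the device more.

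This affects the single primary test and the between-arm comparisons of biomarkers, sleep, quality of life, mood and pain.

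**Working it through.** **The plan's own figure.** Sample size justification and power gives 0.93 for a difference of 7, SD 9, 40 per arm. The noncentrality is (7/9) × √(40/2) = 3.478, and two-sided power is Φ(3.478 − 1.960) = 0.936 (0.930 with the t distribution). The figure reproduces. It contains no covariate term, so removing compliance leaves it unchanged.

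**What adjustment does.** In a least-squares fit of PASAT on arm and compliance,

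adjusted coefficient = (difference in mean PASAT) − b × (difference in mean compliance),

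where b is the pooled within-arm slope of PASAT on compliance. The first term estimates the effect of assignment. The adjusted coefficient therefore agrees with it on average only if mean compliance is equal between arms or b is zero.

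**Inputs for an illustration.** From the documents: SD 9, difference 7, 100 patients randomised 1:1 (50 per arm), one-sided 0.05. Assumed: compliance entered as yes/no; 60% of the PAP arm compliant, in line with the 40% allowed for non-adherence and/or loss; sham compliance varied; correlations as stated below, taken as remaining after the other covariates. Rejection rates come from simulation with 20,000 replicates per scenario.

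**1. A true gain of 7 in compliant PAP users only.** The effect of assignment is 0.6 × 7 = 4.2, with unadjusted power of 69–73%. With no shared cause and compliance proportions p1 (PAP) and p0 (sham),

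b = 7 × p1(1 − p1) / [p1(1 − p1) + p0(1 − p0)].

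- Sham 50%: b = 7 × 0.24/0.49 = 3.43; coefficient 4.2 − 3.43 × 0.1 = 3.86
- Sham 40%: b = 7 × 0.24/0.48 = 3.50; coefficient 4.2 − 3.50 × 0.2 = 3.50
- Sham 30%: b = 7 × 0.24/0.45 = 3.73; coefficient 4.2 − 3.73 × 0.3 = 3.08

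The shared-trait columns add a trait correlated 0.6 with compliance and 0.3–0.5 with PASAT.

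| Sham compliant | Adjusted coefficient, no shared cause | Power | Adjusted coefficient, shared trait | Power |
|---|---|---|---|---|
| 60% | 4.2 | 74% | 4.2 | 74–76% |
| 50% | 3.9 | 67% | 3.4–3.6 | 60–62% |
| 40% | 3.5 | 58% | 2.6–3.0 | 41–48% |
| 30% | 3.1 | 47% | 1.8–2.3 | 24–33% |

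**2. No true effect, same shared trait.** Here b = 9 × r_c × r_y × [φ(z1) + φ(z0)] / [p1(1 − p1) + p0(1 − p0)]. The r terms are the trait's correlations with compliance and PASAT, and φ(z) is the normal density at each arm's compliance threshold. For 40% PAP versus 60% sham with correlations 0.6 and 0.5, b = 9 × 0.3 × (0.386 + 0.386)/0.48 = 4.35. The coefficient is shifted by −4.35 × (0.4 − 0.6) = +0.87 points.

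| PAP vs sham compliant | False-positive rate |
|---|---|
| 40% vs 60% | 8–12% |
| 45% vs 55% | 7–8% |
| 50% vs 50% | 5% |
| 55% vs 45% | 3–4% |
| 60% vs 40% | below 3% |

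With both correlations at 0.3, the first two rows are close to 6%. With no shared cause the rate stays at about 5% in every row. The unadjusted test stays at about 5% throughout.

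**3. Compliance as hours.** Assume a total effect of 7, a slope of 1.5 points per hour, and PAP raising use by 1 hour. The adjusted coefficient is then 7 − 1.5 × 1 = 5.5. The form of the covariate does not alter the conclusion.

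**The case against.** The strongest reply is that the distortion is conditional. With equal mean compliance the adjusted coefficient matches the unadjusted one and power is slightly higher. The design also works towards equal use: participants and coordinators are blinded, and low use is followed up in both arms. This is correct as far as it goes, but neither feature guarantees equal use between an auto-titrating device and a fixed 3 cmH2O sham, and randomisation does not balance something that happens afterwards.

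Some textual support is soft. The remark that "Auto-PAP has been successfully used in several patient populations and may improve compliance with PAP" sits in a paragraph justifying auto-titration and does not compare PAP with sham. The aim to "identify whether compliance influences health-related outcomes" is a question, not a claim. Neither is needed, because the Primary Hypothesis section itself includes compliance on the ground that it may influence PASAT.

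Type I error rises only if sham users comply more. If PAP users comply more, the test is conservative and the main risk is lost power. That stands, but the direction is unknown when the plan is fixed.

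The secondary tests are exploratory. Mood and pain are both outcomes there and covariates in the primary model, so reuse may not be literal. That is fair, but no alternative model is written down.

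The per-protocol repeat is a separate analysis and leaves the primary test as it is.

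**Conclusion.** The concern holds. A post-randomisation variable is committed to the primary test, no primary model omits it, and this does not fit the plan's own intention-to-treat statement. The tested coefficient equals the effect of assignment only under conditions that the plan neither states nor can secure.

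That conclusion rests on the text and the regression identity. The sizes are illustrations, because the documents give no compliance by arm and no correlations. Under the assumptions shown, a true 4.2-point effect shrinks to between 3.9 and 1.8 points when sham compliance is 10 to 30 percentage points lower, and power falls to between 67% and 24%. Under no effect, the false-positive rate ranges from below 3% to about 12%, and bias is at most about 0.9 points. The problem must be fixed because it affects the primary inference.

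**What to change.** Delete compliance with PAP from the covariates of the primary model and from every between-arm secondary model based on it, including those at one month. Add a clause stating that the remaining covariates take values measured before randomisation. This clarification matters mainly for pain and anxiety or depression: the section Sleep, Quality of Life, and Mood has mood and pain measured again at four months, and the primary model does not say which values it uses.

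Examine compliance only in analyses labelled supplementary. The per-protocol repeat already planned can serve, with a note that it too selects on behaviour after randomisation. A complier-average causal effect, with its exclusion restriction stated, is an optional addition.

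The cost is one covariate removed and one clause added. No data, visits or sample size change, and the stated power of 0.93 is unaffected.
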